[H2a] Perceived CVD and diabetes risks, perceived life expectancies and subjective survival probabilities are correlated with objective risks predicted from risk factors, including demographics, BMI etc.

Test:

- Regress perceived personal risks from both information treatment group and control group on 10year CVD risk predicted from Globorisk, 10-year diabetes risk predicted from Finnish Diabetes Risk Score (FINDRISC) (Lindstrom and Tuomilehto 2003) and lifetable survival probabilities.³
- Data from section D prior to treatment group receiving information on personal CVD risk.

[H2b] Perceived CVD and diabetes risks, and perceived life expectancies, deviate from predicted risks due to differential weighting of risk factors.

Test:

- Regress perceived personal risks of both information treatment group and control group (section D) on risk factors and compare coefficients with those obtained from regression of predicted probabilities on risk factors. For example, for personal 10-year CVD risk, compare coefficients from model of reported probability to those used in Globorisk risk prediction tool to produce predicted probabilities. Moreover, compare other coefficients to those found in previous literature on the determinants of CVD and diabetes risks, and on life expectancies, such as, family history and exercise.
- Regress perceived personal CVD and diabetes risks, life expectancies and subjective survival probabilities (section D) on the respective perceived base rates (section B) and on risk factors to test the extent to which perceived personal risks are based on perceived base rates with an adjustment to make use of information available to the respondent on risk factors.

[H2c] Perceived base rates for CVD, diabetes, life expectancy and survival probability are higher than objective (predicted) base rates.

Tests:

- Compute mean deviations of perceived base rates (section B) from predicted base rates. A positive (negative) mean deviation hints at overestimation (underestimation) of CVD prevalence/diabetes prevalence/life expectancy/survival probability.
- Compute mean ratios of perceived base rates to objective (predicted) base rates. A mean ratio > 1 (< 1) hints at overestimation (underestimation) of CVD prevalence/diabetes prevalence/life expectancy/survival probability.
- Compare proportion of sample with perceived base rate < objective (predicted) base rate with proportion with perceived base rate > objective base rate.

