³ This test could be conducted using all survey respondents, including those in the lottery intervention arm. The reason we exclude the latter is because later tests make use of the information intervention and we want to have a consistent sample throughout.

[H2d] The accuracy of base rate estimates varies with education, personal risks, life expectancies and survival probabilities, the respondent's confidence in the accuracy of his perceived base rate, the respondent's degree of worry about CVDs, the respondent's degree of dispositional optimism, and possibly other characteristics.

Tests:

- Repeat computation of mean deviations and mean ratios as explained in [H2c] for each gender/age category combination and check whether CVD/diabetes prevalence, life expectancy and survival probabilities are systematically (by factors defined in [H2d]) over- or underestimated.
- Regress mean square estimation error ((perceived predicted)²) and binary indicator of whether base rate has been over- or underestimated on education level, predicted personal CVD/diabetes risk, predicted life expectancies and survival probabilities, confidence about own base rate estimates, worry about CVDs, dispositional optimism, and possibly other characteristics.

[H2e] Perceived personal CVD risk is negatively correlated with perceived life expectancies and survival probabilities.

- Regress perceived personal CVD risk on perceived life expectancies and on survival probabilities until the age of 80 years (section D).
- Compute fraction of respondents who state a perceived life expectancy conditional on experiencing a CVD event lower than their unconditional perceived life expectancy.

[H2f] Perceived personal CVD and diabetes risks, life expectancies and subjective survival probabilities deviate systematically from base rates with a tendency towards optimism bias.

Tests:

- Compute mean deviations of prior perceived personal risk (section D) from predicted base rate for treatment and control group. A negative mean deviation is consistent with optimism bias.
- Compare the mean deviation of the treatment group that is given information on the base rate (section C) with the control group that is not. Establish the extent to which under-/over-estimation of the base rate contributes to apparent optimism/pessimism bias.
- Compute mean ratio of perceived personal risk to predicted base rate for treatment and control group. A mean ratio < 1 is consistent with optimism bias.

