- Compare proportion of sample with perceived personal risk < base rate with proportion with perceived personal risk > base rate for treatment and control group. This does not suffer from the same sensitivity to outliers as the two measures proposed immediately above.
- Repeat the mean deviation test for an event with positive valence and similar average risk as 10year CVD risk. For this we use the probability of living past the age of 80 (section D). A positive mean deviation in this case would be consistent with pessimism bias. If we find this, then we cannot conclude that positive mean deviation in previous test is indicative of optimism bias.

- Test whether control group individuals state lower perceived personal risks (section D) than perceived base rates (section B) given not provided with base rate information.
- Compute share of unrealistically optimistic, accurate and unrealistically pessimistic individuals according to the definitions of Radcliffe and Klein (2002). Test whether there are significantly more unrealistically optimistic than unrealistically pessimistic individuals.
 - In particular, compute the ratio of predicted personal CVD risk to predicted CVD base rate (Globorisk), as well as the ratio of perceived personal CVD risk (section D) to perceived CVD base rate (section B). Individuals who provide a perceived risk ratio of more than 10% lower than their predicted risk ratio are defined as unrealistically optimistic. Likewise, individuals who consider themselves to be at higher relative risk than their predicted risk ratio (by more than 10%) are considered unrealistically pessimistic. Individuals whose perceived relative risk is within 10% of their predicted risk ratio are considered accurate.
 - Since a ratio is affected more by noise at small values than at large values, we will also define optimism / pessimism in terms of the difference between perceived personal and base rate CVD risk in comparison with the difference in the respective predicted risks.

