[H2g] Individuals high in dispositional optimism, high in comparative optimism, and low in unrealistic optimism have the most favorable profile with respect to health, anxiety and knowledge. In particular, we expect that these individuals exhibit the best health status and lowest risk factor levels, have the lowest predicted risks of having a heart attack or a stroke within 10 years, worry the least about this risk and have the highest CVD risk factor knowledge (see Radcliffe and Klein, 2002).

Test:

- Regress health status, risk factor levels, predicted 10-year personal CVD risks, worry about CVD risk and risk factor knowledge on the degree of dispositional optimism, a binary variable representing comparative optimism and a binary variable representing unrealistic optimism.
- Unrealistic optimism is computed as described in [H2f] following Radcliffe and Klein (2002). Comparative optimism is a binary variable indicating whether an individual stated a lower perceived personal risk than his/her respective perceived base rate.
- Test whether coefficients of dispositional, comparative and unrealistic optimism are consistent with the hypothesis.

[H2h] Dispositional optimists possess more optimistic risk perceptions, but not more optimistically biased risk perceptions. In particular, dispositional optimism is positively correlated with comparative optimism, but uncorrelated with unrealistic optimism (see Radcliffe and Klein, 2002).

Test:

- Measure correlation between dispositional optimism and comparative optimism.
- Measure correlation between dispositional optimism and unrealistic optimism according to definition of Radcliffe and Klein (2002) (see [H2f]).

[H2i] Individuals understand that they can decrease their personal CVD risk by improving their risk factor profile.

Test:

- Compute fraction of respondents who report a personal CVD risk conditional on reducing exposure to risk factors (i.e. smoking, BMI and blood pressure) (section H) smaller than their perceived unconditional personal CVD risk (F_T and D_C). Test whether this fraction is higher for treatment than for control group.
- Regress binary variable indicating a perceived personal CVD risk conditional on reduced exposure to risk factors smaller than the perceived unconditional personal CVD risk on knowledge about CVD risk factors. Test whether individuals with a higher CVD risk factor knowledge are more likely to state a conditional risk smaller than their unconditional risk.

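### H2f: the sign rule for the living-past-80 check is reversed relative to the CVD test that it repeats

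*Combined protocol and SAP*

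**What the plan says.** All the relevant text is in section 3.2 of the combined protocol and SAP.

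- **H2f, first test (CVD).** "Compute mean deviations of prior perceived personal risk (section D) from predicted base rate for treatment and control group". The reading follows: "A negative mean deviation is consistent with optimism bias".
- **H2f, ratio version.** With perceived personal risk over predicted base rate: "A mean ratio < 1 is consistent with optimism bias".
- **H2f, check on a desirable event.** "Repeat the mean deviation test for an event with positive valence and similar average risk as 10year CVD risk". The event is living past 80. The plan then says: "A positive mean deviation in this case would be consistent with pessimism bias". If that is found, "then we cannot conclude that positive mean deviation in previous test is indicative of optimism bias".
- **H2c, a related test on perceived base rates.** "A positive (negative) mean deviation hints at overestimation (underestimation) of CVD prevalence/diabetes prevalence/life expectancy/survival probability".
- **H2g, definition.** "Comparative optimism is a binary variable indicating whether an individual stated a lower perceived personal risk than his/her respective perceived base rate".

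The bullet on living past 80 gives no new subtraction order.

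**The concern.** The check exists to separate real optimism from a general tendency to report probabilities that are too low (or too high). For an undesirable event such as CVD, stating a personal chance below the base rate is optimistic. For a desirable event such as living past 80, stating one below the base rate is pessimistic. Someone who understates every probability therefore looks optimistic about CVD and pessimistic about survival, and the second result should warn the analyst against trusting the first.

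That logic is sound, but the signs written for it are the wrong way round under the definition being repeated. H2f puts forward optimism bias for survival probabilities as well as for CVD risk, and this bullet is the only place in H2f that attaches an optimism or pessimism label to a signed survival deviation. If the rule stays as written, the analyst must either apply a reversed label or choose a reading after seeing the data.

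**Working it through.** The plan gives no figure to reproduce here. The check is one of signs.

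**Inputs.** Four sign statements, all from section 3.2:

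- S1 (H2c): positive deviation = overestimation, with survival probability named.
- S2 (H2f, CVD test): negative CVD deviation = optimism.
- S3 (H2f, living past 80): positive survival deviation = pessimism.
- S4 (H2f, living past 80): positive CVD deviation = the possible optimism signal. The sentence presupposes this rather than asserting it.

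**Step 1: try both subtraction orders.**

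| Statement | d = perceived − base | d = base − perceived |
|---|---|---|
| S1 | true | false |
| S2 | true | false |
| S3 | false | true |
| S4 | false | true |
| Total true | 2 of 4 | 2 of 4 |

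Neither order satisfies all four. The two sentences on living past 80 agree with each other, but only under the order opposite to the one that S1 and S2 require.

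**Step 2: use the rules that do not depend on subtraction order.** The ratio rule makes perceived/base < 1 optimism for CVD, so perceived is below base. Comparative optimism in H2g also means a personal risk stated below the (perceived) base rate. Both point the same way as S2 with d = perceived − base, so S3 and S4 are the ones to correct.

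**Step 3: confirm that the sign does not depend on the survival base rate.** The documents give no base rate for living past 80, so 10%, 30% and 50% were assumed. With d = perceived − base, a report 5 points above base gives d = +5 (optimism) and one 5 points below gives d = −5 (pessimism) at all three. For CVD at a base of 11.35% (section 10.1), 6.35 − 11.35 = −5 is optimism and 16.35 − 11.35 = +5 is pessimism.

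**Step 4: follow the literal rule through the two patterns that matter** (d = perceived − base).

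| CVD deviation | Survival deviation | What it suggests | What the text as written does |
|---|---|---|---|
| − | + | Optimism on both events | Labels the survival result pessimism |
| − | − | Possible general under-reporting | Gives no caution: the trigger needs a positive survival deviation, and the caution covers only a positive CVD deviation |

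**Illustration only.** Set both base rates at 11.35%. This is an assumption: the plan says only that the two events have similar average risk. Take a respondent who is optimistic by an assumed 20% on both:

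- CVD: 0.8 × 11.35 = 9.08, so d = 9.08 − 11.35 = −2.27 points.
- Survival: 1.2 × 11.35 = 13.62, so d = 13.62 − 11.35 = +2.27 points, which the plan would call pessimism.

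At an assumed 10% the deviations are ±1.135 points, and at 30% they are ±3.405. The mislabelling is the same.

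**Step 5: see what other protection exists.** Suppose every probability is reported at 0.8 of its value.

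- H1a complementarity: 0.8p + 0.8(1 − p) = 0.8, not 1, so H1a flags it.
- Unrealistic optimism by ratios: (0.8 × personal)/(0.8 × base) = personal/base, so the respondent is still classed as accurate.
- Control-group comparison of personal risk (section D of the risk module) with perceived base rate (section B): the difference is scaled by 0.8 and keeps its sign.

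These three tests are unaffected by the error.

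**The case against.** The strongest reply is that this is a wording slip. The intended logic can be recovered, the bullet itself says that the event is desirable, and the neighbouring rules fix the direction. A careful analyst would probably see the intent, and no model or test statistic changes. All of that stands, and it limits the importance of the point. It does not remove the contradiction, because the text is a stated interpretation rule, and nothing in the documents gives the reversed order for this test.

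Three narrower objections are also fair:

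- The second sentence on living past 80 only denies a conclusion, so under perceived − base it is literally true but empty. The firm clash is between S2 and S3, and the 2-of-4 count treats a presupposition as a statement.
- H2c compares perceived base rates, not personal risk, with predicted base rates. It supports the sign convention by analogy and is not the test being repeated.
- The figure of 11.35% is a power-calculation value for CVD, so the illustration shows direction only. The 2.27 points are not an estimate of any effect.

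The conclusion survives all three, since it needs only the CVD test, the ratio rule and the instruction to repeat the test for a desirable event.

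**Conclusion.** The concern holds. The sign rule for the living-past-80 check contradicts the H2f test that it repeats: it labels optimism about survival as pessimism and names the wrong CVD sign as the optimism signal. This rests on one reading, that repeating the test keeps its subtraction order. The opposite order does not rescue the text, because it breaks the CVD rule instead.

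The consequence is narrow: the interpretation of one robustness check on baseline beliefs. The principal outcome analysis, the interventions and the sample size are unaffected, and three other tests give some protection against general under-reporting. It should be corrected before the belief data are interpreted, but it does not threaten the trial's main results.

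**What to change.** In the H2f bullet on living past 80, change *positive* to *negative* in both sentences. A negative survival deviation is then the sign of pessimism and, if it is found, a negative CVD deviation can no longer be taken as evidence of optimism bias. With d = perceived − base, all four sign statements then agree, as do the ratio rule and the H2g definition.

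Add one line that defines the deviation as a formula (perceived personal risk minus predicted base rate) and use it throughout H2f, with the same order, perceived minus predicted, in H2c.

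The cost is two words and one line, with no change to data collection, models or sample size. Defining the deviation as base rate minus perceived and reversing the signs in H2c and in the H2f CVD test would also be consistent. That needs more edits and sits less naturally with the ratio rules, so the first option is preferable.

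### H2g regresses predicted CVD risk and its input risk factors on an unrealistic-optimism flag computed from predicted CVD risk, so two of its three optimism coefficients lean towards the hypothesis by construction

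*Combined protocol and SAP*

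**What the plan says.** H2g (section 3.2) expects people high in dispositional optimism, high in comparative optimism and low in unrealistic optimism to have the best profile. Among other things they should "have the lowest predicted risks of having a heart attack or a stroke within 10 years". The test is to "Regress health status, risk factor levels, predicted 10-year personal CVD risks, worry about CVD risk and risk factor knowledge". Three regressors enter this model. Dispositional optimism enters as a score, and the other two are indicators: "a binary variable representing comparative optimism and a binary variable representing unrealistic optimism". No other covariate is named.

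The two binary regressors are defined as follows.

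- **Unrealistic optimism** is taken from H2f. One ratio is Globorisk predicted personal risk over Globorisk predicted base rate. The other is perceived personal risk over perceived base rate. "Individuals who provide a perceived risk ratio of more than 10% lower than their predicted risk ratio are defined as unrealistically optimistic." H2f adds a second version: "we will also define optimism / pessimism in terms of the difference between perceived personal and base rate CVD risk", set against the same difference in predicted risks.
- **Comparative optimism**: "Comparative optimism is a binary variable indicating whether an individual stated a lower perceived personal risk than his/her respective perceived base rate."

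Section 5.2 says the predicted base rate uses age and sex only, while the personal prediction also uses smoking, BMI and blood pressure.

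**The concern.** One outcome, predicted personal risk, is the numerator of the threshold that defines a regressor. Because the base rate uses only age and sex, that threshold moves with smoking, BMI and blood pressure, which are the risk-factor outcomes in the same test. Among people of the same age and sex who state the same beliefs, those with higher predicted risk are more likely to be flagged. H2g treats a positive association between the flag and predicted risk as support.

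The study could therefore report that unrealistic optimists have worse risk profiles, and comparative optimists better ones, when respondents' beliefs contain no information. H2f to H2h give no benchmark, adjustment or caution on this. The difference-based version does not help, since it also contains predicted personal risk. Under H3d the plan does warn against inferring a mechanism for optimism bias from asymmetric updating alone, but H2g carries no similar warning.

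**Working it through.** **Notation.** R = predicted personal risk / predicted base rate. P = perceived personal risk / perceived base rate. UO = 1 if P < 0.9R (reading the 10% as relative). CO = 1 if P < 1. H2g is supported by a positive UO coefficient and a negative CO coefficient.

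**Step 1: what the definitions force.** If P is independent of R, Pr(UO = 1 | R) = Pr(P < 0.9R), which rises with R. With both flags in the model, the cells where they disagree are informative whatever people believe:

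- UO = 1, CO = 0: P ≥ 1 and P < 0.9R, so R > 1/0.9 = 1.11.
- UO = 0, CO = 1: P < 1 and P ≥ 0.9R, so R ≤ P/0.9 < 1.11.

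Everyone flagged only as unrealistically optimistic has a higher R than everyone flagged only as comparatively optimistic. Under the difference version the same argument separates the two cells at R = 1. This pushes UO up and CO down.

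**Step 2: inputs for the size.** The documents give no power or error rate for H2g, so there is no figure to reproduce.

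- Mean predicted risk 11.35%, SD one fifth of the mean, significance 5% (section 10.1). Taken as two-sided, that is 2.5% in the supporting direction.
- N = 299 + 1,361 = 1,660 (Table 6, binary outcomes, information plus control). Leaving out the lottery arm follows the footnote to H2a; applying it to H2g is a reading of the plan.
- Clustering: ICC 0.1 with 10 per cluster gives a design effect of 1 + 9 × 0.1 = 1.9, and 1,660/1.9 ≈ 874.
- Assumed, because the documents do not give them: log-SD of R 0.1 to 0.35, of the age-sex base rate 0.05 to 0.8, of P 0.3 to 1.0.

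**Step 3: uninformative beliefs.** P was drawn independently of R and of all risk factors, and the planned three-regressor model was fitted by OLS with robust standard errors.

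| Setting (N = 1,660) | UO coefficient on predicted risk | Significant, UO > 0 | Significant, CO < 0 |
|---|---|---|---|
| log-SD of R 0.2, base rate 0.05 | +2.7 to +3.3 points | 100% | 100% |
| log-SD of R 0.2 to 0.35, base rate 0.5 to 0.8 | +2.7 to +6.7 points | 99.5% to 100% | 98% to 100% |
| log-SD of R 0.1, base rate 0.6 | +1.0 to +1.2 points | 30% to 58% | 26% to 35% |

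A second, independent set of runs gave 99% to 100% for UO at log-SD 0.2 to 0.35 and 34% to 82% at 0.1. Across the settings in the table, the UO coefficient was +11.5 to +19.7 mmHg for systolic pressure and +20 to +39 percentage points for smoking, significant in 100% of runs. BMI was not simulated separately. An effective N of 874 and the difference-based flag each gave 100% for predicted risk in the settings run (log-SD of R 0.2 and 0.35). Dispositional optimism stayed near 5%, and worry rejected in 3.5% to 7.7%.

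**Step 4: informative beliefs.** Log P was allowed to respond to log R with slope 0, 0.5, 1 (accurate apart from noise) or 1.5 (over-reaction), with 300 runs per setting. At log-SD of R 0.2 to 0.35, UO was significantly positive in 100% of runs in 11 of 12 settings and 65% in the other. At 0.1 it was 28% to 39%. Separate runs at slope 1.5 with low noise gave 74% and 23%, with the coefficient still positive.

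**Step 5: without the flag.** Under uninformative beliefs, regressing predicted risk on log P rejected in 4.3% to 5.7% of runs (1% to 8% in the second set). CO and dispositional optimism without UO gave 4.6% for CO.

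**The case against.** The strongest counter-argument is that the sign depends on how beliefs respond to risk. In a plain comparison of flagged with unflagged respondents this is true: the difference is about zero when beliefs are proportional to predicted risk and negative (-0.4 to -4.2 points) when they over-react. A reader might also go too far the other way and infer that H2g cannot fail. The documents do not support that either. Significance is not assured when R varies little, or when beliefs over-react with little noise. H2g is also a joint statement about three optimism measures and several outcomes. The dispositional-optimism coefficient is not circular, nor are worry and risk-factor knowledge. What does not stand is the defence of the planned model itself: with comparative optimism included, the unrealistic-optimism coefficient stays positive in all the belief scenarios examined.

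It can also be said that H2g is one non-randomised belief analysis among many and follows a published definition. That limits the weight of the point but does not remove the circularity.

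**Conclusion.** The point holds for predicted CVD risk, blood pressure, BMI and smoking. For these outcomes the unrealistic- and comparative-optimism coefficients cannot separate H2g from uninformative, accurate or over-reactive beliefs. The direction of the push follows from the definitions. Its size rests on assumed spreads: false support for predicted risk in about 99% to 100% of runs at log-SD of R 0.2 to 0.35, and about 30% to 80% at 0.1, against 2.5% nominal.

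Health status is affected only as far as it correlates with the risk factors. A reader might infer that the trial's main results are compromised. They are not: the principal outcome, the treatment-effect analyses and the sample size do not use this flag.

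**What to change.** For predicted CVD risk, blood pressure, BMI and smoking, remove the unrealistic-optimism flag in both its ratio and difference versions. Regress these outcomes on the perceived risk ratio (or the comparative-optimism indicator) and dispositional optimism. State that an unrealistic-optimism coefficient on these outcomes will not count as support for H2g. Keep the flag for worry, knowledge and health status, and for health status also report a version adjusted for predicted CVD risk.

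A permutation benchmark, shuffling perceived ratios and requiring the observed coefficient to exceed the shuffled ones, should not be the criterion. It is close to nominal when beliefs are uninformative (6.0% against 5%, 200 runs), but H2a expects beliefs to track predicted risk. In simulations with a belief slope of 0.5 or more, the coefficient exceeded the upper permutation limit in no run. At slope 1 it fell below the lower limit in 20% to 100% of runs. The benchmark is therefore biased against H2g.

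The cost is SAP wording and a few lines of code, with no new data. The real loss is that H2g no longer tests unrealistic optimism against predicted risk and risk factors, and what remains overlaps with H2a and H2b.
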